8.2. Additional Immunogenicity Analyses

Further immunogenicity analyses (see Section 3.2.2 for planned sets of assays) will be considered exploratory for testing purposes (see Section 5.8 for how significance and multiplicity will be handled), but they will otherwise follow a similar process as the primary immunogenicity analysis. For assays that are not conducted via titer experiments, the analysis values will be handled as log GMTs are, after appropriate transformation of the data to be

approximately normal when necessary; instead of RCD curves, boxplots will show the assay values for each group, by visit.

The kinetics of log IgG titers over time will be assessed via generalized estimating equations (GEE) models, with the immune response appropriately-transformed to assume normally-distributed error terms and RV546 vaccine dosage, adjuvant, study day, and all 2- and 3-way interactions included as covariates. These covariates will be assessed for significance at the 1%-level, and any findings will be considered hypothesis-generating. An unstructured working covariance matrix will be preferred, but other choices may be necessary due to computational challenges or poor model fit. These details will be described in the final report. Similar models may be fit for other assays, and these would also be considered exploratory.

To assess the relationship between possible confounders and the appropriately-transformed titers at the primary endpoint time point, a linear regression model will be fit as well, adjusting for vaccination group, age, sex, RV306 vaccination group, and time between final RV306 vaccination and RV546 vaccination. Covariates will be assessed for significance at the 1%-level, and again findings will be considered hypothesis-generating. Similar models may be fit for other assays also.

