		xx	xx.x (xx.x, xx.x)	xx	xx.x (xx.x, xx.x)	xx	xx.x (xx.x, xx.x)	xx	xx.x (xx.x, xx.x)	xx	xx.x (xx.x, xx.x)	0.xx
[Additional visits or Peak]		xx	xx.x (xx.x, xx.x)	xx	xx.x (xx.x, xx.x)	xx	xx.x (xx.x, xx.x)	xx	xx.x (xx.x, xx.x)	xx	xx.x (xx.x, xx.x)	0.xx

Note: N = Number of participants in the Immunogenicity Population; n = Number of participants with available samples
^aANOVA used to compare log titer group means across all vaccination groups

Note: This will be adapted for assays with continuous analysis values, as appropriate

Table 33: Pairwise Comparisons of Geometric Mean Titers Between Vaccination Groups, by Visit and Antigen – [Assay name]

Visit	Antigen	Comparison	p-value ^a	Adjusted p-value ^b
Visit 2 (Day 1)	gp120A244gD-D11	Full IHV01/A244 vs. Placebo	0.xx	0.xx
		Fractional IHV01/A244 vs. Placebo	0.xx	0.xx
		Full IHV01/A244 + ALFQ vs. Placebo	0.xx	0.xx
		Fractional IHV01/A244 + ALFQ vs. Placebo	0.xx	0.xx
		Full IHV01/A244 vs. Fractional IHV01/A244	0.xx	0.xx
		Full IHV01/A244 vs. Full IHV01/A244 + ALFQ	0.xx	0.xx
		Full IHV01/A244 vs. Fractional IHV01/A244 + ALFQ	0.xx	0.xx
		[Additional pairwise comparisons]	0.xx	0.xx
	[Additional antigens]			
[Additional visits or Peak]				

^aTwo-sided t-test used to compare log titer group means^bStep-down Bonferroni-Holm procedure used

Table 34: Collapsed Comparisons of Geometric Mean Titers, by Visit and Antigen – [Assay name]

Visit	Antigen	Full IHV01/A244 (N=X)		Fractional IHV01/A244 (N=X)		p-value ^a	ALFQ (N=X)		No ALFQ (N=X)		p-value ^a
		n	GMT (95% CI)	n	GMT (95% CI)		n	GMT (95% CI)	n	GMT (95% CI)	
Visit 2 (Day 1)	gp120A244gD-D11	xx	xx.x (xx.x, xx.x)	xx	xx.x (xx.x, xx.x)	0.xx	xx	xx.x (xx.x, xx.x)	xx	xx.x (xx.x, xx.x)	0.xx
	[Additional antigens]										
[Additional visits or Peak]											

Note: N = Number of participants in the Immunogenicity Population; n = Number of participants with available samples

^aTwo-sided t-tests used

Table 35: GEE Model to Evaluate the Longitudinal Immune Response and Relationship with Vaccine Dosage and Adjuvant – [Assay name]

Model Parameter	Value	Parameter Estimate	SE	p-value
Intercept	Intercept	XXX.X	XXX.X	X.XXX
Vaccine Dosage	Fractional Dose (reference)			
	Full Dose	XXX.X	XXX.X	X.XXX
Adjuvant	None (Reference)			
	ALFQ	XXX.X	XXX.X	X.XXX
Study Day	Day 0 (Reference)			
	Day 14	XXX.X	XXX.X	X.XXX
	Day 168	XXX.X	XXX.X	X.XXX
	Day 336	XXX.X	XXX.X	X.XXX
Dosage*Adjuvant Interaction	[All interaction levels]	XXX.X	XXX.X	X.XXX
		XXX.X	XXX.X	X.XXX

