Dosage*Study Day Interaction	[All interaction levels]	XXX.X	XXX.X	X.XXX
Adjuvant*Study Day Interaction	[All interaction levels]	XXX.X	XXX.X	X.XXX
Dosage*Adjuvant*Study Day Interaction	[All interaction levels]	XXX.X	XXX.X	X.XXX
Note: N=[XXX] participants in the Immunogenicity Population with results available for at least one post vaccination visit included in the GEE model.				

Table 36: Linear Regression Model to Evaluate the Relationship Between the Immune Response and Potential Confounders– [Assay name]

Model Parameter	Value	Parameter Estimate	SE	p-value
Intercept	Intercept	xxx.x	xxx.x	x.XXX
Biological Sex	Male (Reference)			
	Female	xxx.x	xxx.x	x.XXX
Time from Final RV306 Dose to RV546 Dose	Years (Continuous)	xxx.x	xxx.x	x.XXX
RV306 Vaccination Group	Group 2 (Reference)			
	Group 3	xxx.x	xxx.x	x.XXX
	Group 4A	xxx.x	xxx.x	x.XXX
	Group 4B	xxx.x	xxx.x	x.XXX
Vaccination Group	Placebo (Reference)			
	Fractional IHV01/A244	xxx.x	xxx.x	x.XXX
	Full IHV01/A244	xxx.x	xxx.x	x.XXX
	Fractional IHV01/A244 + ALFQ	xxx.x	xxx.x	x.XXX
	Full IHV01/A244 + ALFQ	xxx.x	xxx.x	x.XXX
Note: N=[XXX] participants in the Immunogenicity Population with results available included in the model.				

Table 37: Seroconversion Percentages by Visit, Antigen, and Vaccination Group – [Assay name]

Visit	Antigen	Full IHV01/A244 (N=X)		Fractional IHV01/A244 (N=X)		Full IHV01/A244 + ALFQ (N=X)		Fractional IHV01/A244 + ALFQ (N=X)		Placebo (N=X)		p-value ^a
		n	Estimate (95% CI)	n	Estimate (95% CI)	n	Estimate (95% CI)	n	Estimate (95% CI)	n	Estimate (95% CI)	
Visit 2 (Day 1)	gp120A244gD- D11	xx	xx.x (xx.x, xx.x)	xx	xx.x (xx.x, xx.x)	xx	xx.x (xx.x, xx.x)	xx	xx.x (xx.x, xx.x)	xx	xx.x (xx.x, xx.x)	0.xx
	[Additional antigens]	xx	xx.x (xx.x, xx.x)	xx	xx.x (xx.x, xx.x)	xx	xx.x (xx.x, xx.x)	xx	xx.x (xx.x, xx.x)	xx	xx.x (xx.x, xx.x)	0.xx
[Additional visits]		xx	xx.x (xx.x, xx.x)	xx	xx.x (xx.x, xx.x)	xx	xx.x (xx.x, xx.x)	xx	xx.x (xx.x, xx.x)	xx	xx.x (xx.x, xx.x)	0.xx
		xx	xx.x (xx.x, xx.x)	xx	xx.x (xx.x, xx.x)	xx	xx.x (xx.x, xx.x)	xx	xx.x (xx.x, xx.x)	xx	xx.x (xx.x, xx.x)	0.xx

Note: N = Number of participants in the Immunogenicity Population; n = Number of participants with available samples

^aExact binomial tests used to compare proportions across all vaccination groups

Table 38: Pairwise Comparisons of Seroconversion Percentages Between Vaccination Groups, by Visit and Antigen – [Assay name]

Visit	Antigen	Comparison	p-value ^a	Adjusted p-value ^b

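### In the exploratory GEE table (SAP Table 35), the Dosage, Adjuvant and Dosage*Adjuvant rows are pre-vaccination contrasts, and the Dosage*Day and Adjuvant*Day rows each use only two of the four active groups

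*SAP*

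**What the plan says.** SAP 8.2 (Additional Immunogenicity Analyses) describes a GEE for log IgG titer over time, with "RV546 vaccine dosage, adjuvant, study day, and all 2- and 3-way interactions included as covariates". On testing it says: "These covariates will be assessed for significance at the 1%-level, and any findings will be considered hypothesis-generating". On the correlation structure it says: "An unstructured working covariance matrix will be preferred".

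The Table 35 shell in SAP Appendix 1 fixes the coding. The reference levels are "Fractional Dose (reference" for dosage, "None (Reference" for adjuvant and "Day 0 (Reference" for study day, with Days 14, 168 and 336 as the other days. Each interaction block is to print "All interaction levels", with an estimate, SE and p-value per row. The shell has no placebo level. Neither SAP 8.2 nor Table 35 specifies an averaged contrast, a joint test or a baseline constraint for this model.

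Elsewhere, SAP 4.2 calls the design factorial. SAP 5.8 and 8.1 plan separate collapsed comparisons (Groups 1+3 vs 2+4, and 1+2 vs 3+4) by two-sided t-test at 0.025, reported in Tables 31 (AUC) and 34 (titers by visit).

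**The concern.** Table 35 is titled as showing how the longitudinal response relates to dosage and adjuvant. A reader will look first at the rows labelled Full Dose and ALFQ. Under the printed coding, neither can show a vaccine effect, because both describe Day 0. SAP 3.3 defines baseline as the last value before vaccination, and the Table 32 shell labels Day 0 as baseline. Yet the SAP tests these rows at 1% along with every other term.

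The ALFQ row is the more exposed of the two. Groups 3 and 4 enroll only after Groups 1 and 2 are complete (SAP 4.1), from a newly generated set of assignments (SAP 4.4.2). A Day 0 difference between Groups 4 and 2 could therefore reflect enrollment stage.

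The rows that do carry information about response, Dosage*Day and Adjuvant*Day, are simple effects at one level of the other factor. They do not match the comparisons the trial names as of interest, and they are less precise.

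**Working it through.** **Meaning of the rows.** Let D = 1 for full dose, A = 1 for ALFQ, and t = 14, 168 or 336. Then Group 1 is (D=1, A=0), Group 2 is (0,0), Group 3 is (1,1) and Group 4 is (0,1). Write Δg for the mean change from Day 0 to Day t in Group g. With reference coding and all interactions:

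- Dosage: b_D = Group 1 − Group 2 at Day 0
- Adjuvant: b_A = Group 4 − Group 2 at Day 0
- Dosage*Adjuvant: b_DA = (Group 3 − Group 4) − (Group 1 − Group 2) at Day 0
- Dosage*Day: b_Dt = Δ1 − Δ2
- Adjuvant*Day: b_At = Δ4 − Δ2
- Dosage*Adjuvant*Day: b_DAt = (Δ3 − Δ4) − (Δ1 − Δ2)

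The first three rows are pre-vaccination contrasts because Day 0 is the reference. The next two use only two groups because Fractional and None are the references and the 3-way term is in the model. Only the 3-way rows use all four groups for the response.

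**Check by fitting.** The Table 35 model was fitted by GEE to one simulated data set of 4 × 16 participants and four visits, with complete data.

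- Dosage row: 0.0442, equal to Group 1 − Group 2 at Day 0.
- Adjuvant row: −0.1516, equal to Group 4 − Group 2 at Day 0.
- Dosage*Day 14: 0.4066 = Δ1 − Δ2.
- Adjuvant*Day 14: 0.5676 = Δ4 − Δ2.
- Exchangeable and unstructured working covariances gave the same estimates and robust SEs.
- Adding heavy noise to all Group 3 and 4 values left Dosage*Day 14 unchanged (0.4066, robust SE 0.2219).

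**Variance.** Let s be the SD of change, equal across groups, with 16 per group.

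- Simple effect: s²(1/16 + 1/16) = 0.125 s²
- Averaged effect, ½[(Δ1 − Δ2) + (Δ3 − Δ4)]: ¼ × 4 × s²/16 = 0.0625 s²

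The variance ratio is 2 and the SE ratio is √2 = 1.41. In the simulated data, robust SEs at Day 14 under reference coding and centred coding were 0.2219 and 0.1543 for dose (ratio 1.44), and 0.1749 and 0.1543 for ALFQ (ratio 1.13). Robust SEs follow the observed group variances, so a single data set scatters around 1.41.

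**The plan's own figures.** The SAP's Table 4 gives detectable differences at 80% power and two-sided 5% of 1.02 SD (16 vs 16), 0.71 SD (32 vs 32) and 0.79 SD (64 vs 16). Noncentral-t power for a two-sample t-test gives 1.024, 0.711 and 0.793, so they reproduce.

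**Power at the GEE's 1% level**, using the same t-test calculation as an approximation to the GEE test:

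| | 16 vs 16 (row as printed) | 32 vs 32 (averaged) |
|---|---|---|
| Detectable difference at 80% power, SD of change | 1.28 | 0.88 |
| Power for 0.71 SD of change | 24.9% | 57.5% |

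**Conversion to single-visit SDs.** The SD of change is the single-visit SD × √(2(1 − ρ)), where ρ is the correlation between Day 0 and Day t. The documents give no ρ, so a range is assumed:

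| Assumed ρ | Factor | Power for 0.71 single-visit SD, 16 vs 16 / 32 vs 32 | Detectable difference at 80%, single-visit SD |
|---|---|---|---|
| 0 | 1.414 | 10.9% / 26.7% | 1.81 / 1.24 |
| 0.3 | 1.183 | 16.6% / 40.5% | 1.51 / 1.04 |
| 0.5 | 1.000 | 24.9% / 57.5% | 1.28 / 0.88 |
| 0.7 | 0.775 | 45.0% / 83.9% | 0.99 / 0.68 |

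**The case against.** The strongest reply is that the factorial effects are tested on the full sample elsewhere. SAP 5.8 makes the collapsed comparisons whether or not pairwise differences appear. Tables 31, 34 and 39 report full vs fractional and ALFQ vs no ALFQ for AUC, titers by visit and seroconversion. At 0.025, 32 vs 32 has about 71% power for 0.71 SD. The AUC is incremental, so Table 31 already compares a rise over time on 32 vs 32. This stands. A reader might infer that the trial tests its dose and ALFQ effects only on 16 vs 16. The documents do not support that; it is true of Table 35 alone.

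The GEE is also exploratory, its reference levels are openly labelled, and Table 32 shows Day 0 GMTs by group with an ANOVA p-value, so a baseline imbalance would be visible. These facts limit the harm. They do not alter what the rows estimate, and calling a finding hypothesis-generating does not help if the row tests a different hypothesis from the one its label suggests.

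Finally, simple effects reported with interaction rows are a legitimate summary, and averaging can hide an interaction. That is fair, and it is why the interaction contrast must be reported beside the averaged ones.

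**Conclusion.** The point holds for Table 35. Three of its row types are Day 0 contrasts that the SAP would test at 1% alongside the response terms. Its two-way day rows are simple effects in Groups 1 vs 2 and 4 vs 2, and no row gives the factorial effect on change from Day 0. The main collapsed conclusions, which rest on Tables 31 and 34, are not affected.

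The factor of two in variance (SE 41% larger) assumes equal variances and complete data. With missing visits, a non-independence working covariance shifts the weights slightly, and model-based SEs would pool variance across groups. The 25% vs 58% comparison is for 0.71 SD of change. In single-visit SDs, which is how SAP 4.4.1 describes variability, it runs from 11% vs 27% (assumed ρ = 0) to 45% vs 84% (assumed ρ = 0.7).

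A reader might also infer that choosing Day 0 as the reference is what halves the sample. It is not: that choice explains only the pre-vaccination rows. Changing the reference day alone would leave the two-way day rows confined to two groups.

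**What to change.** Keep the model in SAP 8.2. In Table 35, for Days 14, 168 and 336 (the last where assayed), report these contrasts of change from Day 0 with estimate, SE and p-value, at the existing 1% hypothesis-generating level:

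- full minus fractional, averaged over ALFQ: b_Dt + ½ b_DAt
- ALFQ minus no ALFQ, averaged over dose: b_At + ½ b_DAt
- their interaction: b_DAt

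In the simulated fit, the Day 14 values are 0.4066 + ½(−0.0735) = 0.370 for dose and 0.5676 + ½(−0.0735) = 0.531 for ALFQ, matching the centred-coding estimates.

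Label the Dosage, Adjuvant and Dosage*Adjuvant rows as baseline (Day 0) checks, and state in SAP 8.2 that they are not tested as vaccine effects.

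The cost is a few contrast statements and a revised shell, with no new data. The downside is nine contrasts per outcome (three effects by three days), and averaged effects that must be read alongside the interaction contrast.

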APPENDIX 2. FIGURE MOCK-UPS**LIST OF FIGURES**

Figure 1:	Study Schematic	5
Figure 2:	CONSORT Flow Diagram	55
Figure 3:	Maximum Severity of Solicited Systemic Reactogenicity Events per Participant Over the Reactogenicity Period, by Vaccination Group	56
Figure 4:	Maximum Severity of Solicited Local Symptoms per Participant Over the Reactogenicity Period by Vaccination Group.....	56
Figure 5:	Frequency of Related Unsolicited Adverse Events by MedDRA® System Organ Class and Vaccination Group	57
Figure 6:	Incidence of Related Adverse Events by MedDRA® System Organ Class and Maximum Severity	58
Figure 7:	Geometric Mean Titer and 95% CI for [specify assay] by Study Day and Vaccination Group.....	59
Figure 8:	Boxplots of [Assay Name] by Vaccination Group.....	60
Figure 9:	Correlation of Peak [Assay Name] Response with Peak [Assay Name] Response by Vaccination Group.....	61

Figure 2: CONSORT Flow Diagram

Figure 3: Maximum Severity of Solicited Systemic Reactogenicity Events per Participant Over the Reactogenicity Period, by Vaccination Group

[figure not shown]
Note: This is an example figure. Vaccination groups will be in separate panels, each systemic event and Any Systemic Reactogenicity will be on the y-axis, and the percent of participants reporting each maximum severity over the entire reactogenicity period will be on the x-axis.

Figures with similar format:

Figure 4: Maximum Severity of Solicited Local Symptoms per Participant Over the Reactogenicity Period by Vaccination Group

[figure not shown]
Note: Vaccination groups will be in separate panels, each local symptom and Any Local Symptom will be on the y-axis, and the percent of participants reporting each maximum severity over the entire reactogenicity period will be on the x-axis.

Figure 5: Frequency of Related Unsolicited Adverse Events by MedDRA® System Organ Class and Vaccination Group

[figure not shown]
Note: Vaccination groups will be in separate panels, each SOC and Any SOC will be on the y-axis, and the total number of events of each severity will be on the x-axis.

Figure 6: Incidence of Related Adverse Events by MedDRA® System Organ Class and Maximum Severity

[figure not shown]

Note: Vaccination groups will be in separate panels, each SOC and Any SOC will be on the y-axis, and the percent of participants reporting each maximum severity will be on the x-axis.

Figure 7: Geometric Mean Titer and 95% CI for [specify assay] by Study Day and Vaccination Group

[figure not shown]

Note: This is an example figure. GMTs and associated 95% CIs are shown on the y-axis and Study Day is shown on the x-axis, with colors and line shapes denoting vaccination group. Similar figures may be generated for collapsed comparisons of ALFQ vs. non-ALFQ groups and fractional vs. full dosing groups. Figures of this type will be presented for titer values. For assays with continuous analysis values, analogous figures will show mean values and associated CIs on the y-axis instead.

Figure 8: Boxplots of [Assay Name] by Vaccination Group

Note: This is an example figure. Visits will be shown in separate panels, where applicable, with separate panels for each visit. Analysis values on the y-axis and vaccination groups along the x-axis. Similar figures may be generated for collapsed comparisons of ALFQ vs. non-ALFQ groups and fractional vs. full dosing groups.

Figure 9: Correlation of Peak [Assay Name] Response with Peak [Assay Name] Response by Vaccination Group

Note: This is an example figure. Groups will be in different shapes and colors, and the Spearman rank-order correlation estimates will be presented for each group in the legend.

APPENDIX 3. LISTINGS**LIST OF LISTINGS**

Listing 1:	Participants Receiving Study Vaccination	63
Listing 2:	Discontinuations and Early Terminations	64
Listing 3:	Participants Not Receiving Assigned Study Vaccination.....	65
Listing 4:	Protocol Deviations	66
Listing 5:	Prior and/or Concurrent Medical Conditions Meeting Exclusion Criteria	67
Listing 6:	Prior and Concomitant Medications Meeting Exclusion Criteria.....	68
Listing 7:	Analysis Populations	69
Listing 8:	Incident HIV Infections	70
Listing 9:	Serious Adverse Events	71
Listing 10:	Non-Serious, Related Unsolicited Adverse Events	72
Listing 11:	Clinical Laboratory Values	73
Listing 12:	Pregnancies.....	74
Listing 13:	Missed Visits, Discontinuations, and Withdrawals Due to COVID-19.....	75

Listing 1: Participants Receiving Study Vaccination

Subject Number	Date of Study Vaccine Administration	Study Group	Injection Site (Left Arm/Right Arm)

Listing 2: Discontinuations and Early Terminations

Subject Number	Study Day of Discontinuation	Reason for Discontinuation	If Due to AE, AE Number	Terminated from Study?

Listing 3: Participants Not Receiving Assigned Study Vaccination

Subject Number	Date of Enrollment	Assigned Study Group	Reason for Termination

Listing 4: Protocol Deviations

Subject Number	Study Group	Deviation Number	Deviation	Study Day
[N/A if screening failure]				

Listing 5: Prior and/or Concurrent Medical Conditions Meeting Exclusion Criteria

Subject Number	Study Group	Exclusion Criterion	Study Day Criterion Met	MedDRA System Organ Class	MedDRA Preferred Term
	[N/A if screening failure]		[N/A if screening failure]		

Listing 6: Prior and Concomitant Medications Meeting Exclusion Criteria

Subject Number	Study Group	Exclusion Criteria	Study Day Criterion(a) Met	Medication Name
	[N/A if screening failure]		[N/A if screening failure]	

Listing 7: Analysis Populations

Subject Number	Study Group	Analysis Population Inclusions	Analysis Population Exclusions (Study Day)

Listing 8: Incident HIV Infections

Subject Number	Study Group	Study Day of Reported HIV Infection	Comments

Listing 9: Serious Adverse Events

Subject Number	Study Group	Adverse Event Number	Adverse Event	Study Day Reported	Duration	Number of Days Post-Vaccination the Event Became Serious	Reason Reported as an SAE	Severity	Relationship to Study Vaccination	If Not Related, Alternate Etiology	Study Vaccine Change	Resolution	Comments

Listing 10: Non-Serious, Related Unsolicited Adverse Events

Subject Number	Study Group	Adverse Event Number	Adverse Event	Study Day Reported	Duration	Severity	Relationship to Study Vaccine	Study Vaccine Change	Resolution	Comments

Listing 11: Clinical Laboratory Values

Subject Number	Study Group	Visit	Actual Study Day	Sex	Age (years)	Laboratory Parameter (Units)	Result (Severity Grade)	Reference Range Low	Reference Range High
						[Units may be +/- or N/A for some lab tests]			

Listing 12: Pregnancies

Subject Number	Study Group	Pregnancy Outcome	Date of Delivery	Date of Termination	If Terminated, Due to a Verified Congenital Anomaly?	Infant Sex	Infant Weight at Birth (g)	Estimated Gestational Age of Infant at Birth (weeks)	Was the Infant Born with Congenital Anomalies?
				[N/A for deliveries]					

Listing 13: Missed Visits, Discontinuations, and Withdrawals Due to COVID-19

Subject Number	Clinical Site	Missed Visits	Reason(s) for Missed Visit (Visit Number)	Participant Discontinued? (Date of Discontinuation)	Reason(s) for Discontinuation	Participant Terminated from Study? (Date of Termination)	Reason(s) for Termination
			e.g. Withdrawn due to positive SARS-CoV-2 test (Visits X, Y)
